Ketamine's tolerability and safety have been demonstrated over almost 5 decades. It has been used as an anesthetic for adults and children since the 1960s and has been used in neuropsychiatric research for more than two decades. Anesthetic doses from 1 to 3 mg/kg are considered to be very safe (Wan et al. 2015). Subanesthetic doses of ketamine (from 0.1 to 2 mg/kg) have been associated with transient side effects including neurocognitive, sensory-motor, and hemodynamic changes. A pooled data study from three different clinical trials of subanesthetic IV ketamine administration in MDD patients found that adverse effects common within the first four hours of administration included dizziness, derealization, and drowsiness. Whether these are truly to be considered 'adverse' or are part and parcel of ketamine's actual effects that result in the antidepressant and/or therapeutic benefits is the subject of much debate. One third of all patients experienced transient hemodynamic changes, particularly elevated blood pressure. There have been no cases of persistent neuropsychiatric sequelae, medical effects, or increased substance abuse in clinical practice. Route of administration and dose provided will also affect tolerability. While there have been multiple reports of dissociative and psychotomimetic effects of ketamine with IV and IM preparations, a trial of sublingual ketamine in 27 MDD patients reported no such side effects (Lara et al., 2013). A trial of intranasal ketamine also found only small increases in dissociative symptoms (Lapidus et al., 2014).

A cautionary here in that increasing dosages of ketamine through any route of administration will result in an increase in dissociative effects.

Ketamine has been approved by regulatory bodies worldwide for use as an anesthetic and an analgesic in both human and veterinary medicine. Ketamine was classified in 1999 as a Schedule 3 substance. Off label use has been a constant in ketamine's history.

Summary of Research Design: This study will be conducted with 4 lactating women who agree to postpone breastfeeding and provide samples of their milk. Ketamine's half-life is variously placed at 2 and a half to 3 hours. The most reliable data puts ketamine's half-life

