at 2.1 hours and for the metabolite—norketamine at 1.2 hours—this from a ketamine study in children indicating the safety of this medicine (Herd et al 2002). Samples will be collected prior to injection for baseline measurement, and timed at 3, 6, and 9 hour intervals--choosing the maximum half-life duration. Two dosages will be administered: 0.5ml/kg and 1.0ml/kg. administered Intramuscularly (IM). Each administration will be separated by a minimum of 3 days and preferably one week.

The study subjects participants to greater than minimal risk because the protocol design calls for administration of IM ketamine. While the safety of IM ketamine administration is well established over decades of use, participants will be provided with full information on risks.

SEE PACKAGE INSERT FOR THIS MANUFACTURER—ATTACHED.

The IM route confers rapid onset—2-5 minutes for effect and a reliable approximate 95% absorption of ketamine. The dosage range for a 50 kg woman amounts to 25-50mg and for a 70kg woman 35mg-70mg, both quantities well within commonly used therapeutic administration of IM ketamine for depression and other psychiatric diagnoses (Dore et al, 2019).

While psychiatric use of ketamine may well exceed 1.0 mg/kg, blood concentrations of ketamine for anesthetic use have tended to follow a linear pattern of concentration, enabling estimates of concentration in breast milk, should there be a decision to exceed 1.0mg /kg IM in clinical practice.

Inclusion Criteria

Obtained by Interview/Self-Report

- • Age 21-45
- • Postpartum with established lactation for a minimum of 3 months.
- • Ability to pump breast milk and to provide a reservoir for infant feeding prior to the study; or acceptance of bottle feeding by the infant.
- • In good health—normal BP/P; afebrile-temp ascertained; review of systems by MD; absence of diagnosed illnesses.
- • Not pregnant--Pregnancy tested for before each administration by urine assay.

Exclusion Criteria:

- • Hypertension with a BP greater than 145/90
- • Subjects must be offAbsence of all psychiatric medications specifically; medications and supplements, or evaluated by the PI for non-interference
- • No alcohol or other substances such as marijuana for 72 hours or more.
- • Weight <50kg or > 90kg.
- • Pregnancy

Method of Subject Identification and Recruitment

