Two of the investigators have close connections to practicing OB/GYNs, one being one of these himself; and the other has a practice with postpartum women in part at a local university medical school. As only 4 subjects will take part, with the possibility of drop-out

requiring further recruitment this 'n' is compatible with the outreach potential of the Investigators. Lactating patients and staff in both situations will be approached for an initial screening conversation.

No advertising is involved.

Procedures

Initial screening for participation will be conducted by an investigator, via telephone.

The IC and Intake form will be emailed/mailed to a potential participant based on the suitability for admission to the study as per the screening determination. The intake form assesses current and previous illnesses, psychiatric conditions, medications, supplements and emergency contacts, etc.

Review of the Intake form will occur prior to the formal Intake Interview to be performed at the site. This review will again determine potential eligibility.

The intake Interview at the site will take place with two investigators present and will take as long as necessary to review the protocol, the IC, the information on the actual Intake form, and to determine admission to the study. This will enable Investigators to screen potential subjects prior to enrollment—as is our general practice. The Informed Consent will be provided along with the Intake Form for review by the subjects prior to making a decision to proceed with the study intake process. Subjects will discuss, and make a decision to sign, or not, the Informed Consent.

HIPAA confidentiality will be maintained throughout. Subjects will be given a numerical designation for all materials, other than the written forms discussed herein. All written and confidential materials will be stored in a locked file on premises available only to the Investigators.

Preliminary lab tests, BP and PR and an initial pregnancy test will be performed.

BP and PR will be performed at 1 hour post-administration to assess peak impact on cardiovascular status.

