This study will assess if the rapid elimination of ketamine facilitates a short and tolerable suspension of breastfeeding. If the study determines that significant amounts of ketamine remain in breast milk after 9 hours and 3 intervals, a decision will be made to add further intervals for assessment. The collection at 3 hour intervals will continue until ketamine levels are undetectable.

No hazardous substances or procedures are involved

Pumping of breast milk will be performed by the subjects, collected, and preserved as per the lab's criteria. Every attempt will be made to collect milk in volume. The study will provide a pump for collection to each participant

Subjects may stay at the clinic for the duration of the collection , or may be provided with instructions and collection materials for at home pumping if the duration is prolonged beyond 9 hours. As much as possible, tThe samples will be collected by the next day.

Subjects will refrain from eating and drinking 3-4 hours before receiving ketamine, this to prevent stomach contents that may contribute to nausea, and reduce any risk of aspiration. Subjects are permitted one cup of coffee if they are caffeine dependent, or juice or water at 3-4 hours prior. Subjects will provide consent for fasting prior to its initiation verbally and later fully in person at the clinic.

A urine pregnancy test will be conducted prior to each administration of ketamine.

A first subject in the study will have milk collected at 0, 3, 6, 9, 12 and 15 hours to determine if these intervals are sufficient to characterize a basic pharmacodynamic profile. If there is a negligible quantity in the samples as the time frame proceeds, the lab will not analyze subsequent samples. Once determined, the study will proceed with the remaining 3 subjects at the intervals projected from the first subject

Two dosages will be administered: 0.5ml/kg and 1.0ml/kg. Intramuscularly (IM). Each administration will be separated by a minimum of 3 days and preferably one week. Each session will follow the same process and procedure as described herein and occur at the study site.

PROCEDURE TIMING CHART

HOUR	PROCEDURE
-30 minutes	Arrives at Study Site Pregnancy Test Review of IC and Fasting with Consent
-!5	BP, HR, Review of Systems
0 Hour	Zero Time Pump
15	IM 0.5mg/kg; or Second Session 1.0mg/kg
15-60	Support for Subject who is reclining on sofa with eyeshades and ambient music

1 hour	BP, HR

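### The protocol says blood-level linearity under anaesthesia allows milk estimates above 1.0 mg/kg, but the study as planned does not check that assumption and could test it only weakly

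*Combined protocol and SAP*

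**What the plan says.** The Summary of Research Design notes that psychiatric doses may go above 1.0 mg/kg. It then states that "blood concentrations of ketamine for anesthetic use have tended to follow a linear pattern of concentration", and draws from this the consequence "enabling estimates of concentration in breast milk, should there be a decision to exceed 1.0mg /kg IM in clinical practice". The sentence carries no citation, slope, dose range or milk data.

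Other parts of the protocol bear on it:

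- **Size.** "This study will be conducted with 4 lactating women who agree to postpone breastfeeding and provide samples of their milk". The recruitment section justifies the number by saying that "this 'n' is compatible with the outreach potential of the Investigators". No precision target is given. Data Storage and Confidentiality allows for more than four subjects.
- **Doses and order.** The Procedure Timing Chart reads "IM 0.5mg/kg; or Second Session 1.0mg/kg", so the higher dose comes second for every woman. On spacing, "Each administration will be separated by a minimum of 3 days and preferably one week".
- **Measurement.** Methods describes assays of ketamine and norketamine in breast milk. No blood drug level is described anywhere. Milk is collected before the dose and at 3, 6 and 9 hours, and also at 12 and 15 hours in the first subject.
- **Analysis.** Data Analysis plans absolute quantities, graphs, and correlations of milk concentration with age, weight, dosage, milk volume and months of breastfeeding. It names no dose ratio, dose-response model or rule for extrapolation.
- **Prior evidence.** Both Purpose and Appendix A state that there are no human milk data.

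**The concern.** The sentence takes two steps without testing either: from linear blood levels to linear milk levels, and from the doses studied to doses above them. The first step needs a milk-to-blood relation that stays constant across dose. The second needs the same relation to continue beyond the range where there are data.

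The protocol's Pharmacology section is more careful. It treats the reassuring neonatal evidence as early and anaesthetic, and leaves the question open for repeated psychiatric use in lactating women.

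At stake is how the results are used. The study is meant to inform how long breastfeeding is suspended, and the protocol expects clinical doses above those it studies. Readers are therefore invited to scale the results up without being told that the scaling is an assumption.

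**Working it through.** The plan states no sample-size, power or precision figure, so there is none to reproduce. The check asks how well the planned data could test proportionality.

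**Inputs from the protocol.** n = 4 women; doses 0.5 and 1.0 mg/kg in each woman; higher dose second; at least 3 days between sessions; half-life taken as 3 hours.

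**Assumed inputs.** Within-woman CV of milk concentration of 20%, 30% or 50%. The documents give no value.

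**1. Precision of the 1.0:0.5 ratio.** For one matched time, or one summary per woman, work on the log scale:

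- s = √ln(1 + CV²)
- SE of the mean log ratio = s·√2/√4
- 95% factor = exp(3.182 × SE), where 3.182 is t with 3 degrees of freedom

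| CV | s | SE | 95% factor | Interval if the observed ratio is 2 |
|---|---|---|---|---|
| 20% | 0.198 | 0.140 | 1.56 | 1.3 to 3.1 |
| 30% | 0.294 | 0.208 | 1.94 | 1.0 to 3.9 |
| 50% | 0.472 | 0.334 | 2.90 | 0.7 to 5.8 |

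With only three evaluable women (t = 4.303), the factors become 2.01, 2.80 and 5.26.

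**2. The same result as a proportionality exponent.** Let C = a·dose^b, where b = 1 is proportional. The half-width for b is ln(factor)/ln 2, which gives 0.64, 0.95 and 1.53. At CV 30%, an observed b of 1 has an interval of about 0.05 to 1.95. If the true b were 1.5 (a ratio of 2^1.5 = 2.83), the power of a paired t-test of b = 1 is 40% at CV 20% and 22% at CV 30%.

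**3. What the assumption contributes above 1.0 mg/kg.** Take 2 mg/kg purely for illustration; it is the top of the subanaesthetic range quoted in the background. Assume within-woman CV 30% and between-woman CV 40%, so s² = 0.0862 and s_b² = ln(1.16) = 0.1484.

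- Proportionality assumed: variance = (0.0862/2 + 0.1484)/4 = 0.0479; factor = exp(3.182 × 0.219) = 2.0.
- Exponent estimated from the study: variance = (5 × 0.0862 + 0.1484)/4 = 0.145; factor = exp(3.182 × 0.381) = 3.4. The 5 is 2² + 1², the weights on the two log means one doubling beyond the top dose.

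The narrower interval comes from assuming b = 1. It contains nothing for the possibility that b differs from 1.

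**4. Fixed order.** If session 2 ran 20% higher for a reason unrelated to dose, b would shift by ln 1.2/ln 2 = 0.26, and a prediction at 2 mg/kg from the fitted exponent would be inflated by 1.2² = 1.44. The 20% is hypothetical. Residual drug is not a plausible cause, since 72 h / 3 h = 24 half-lives.

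**5. Curvature.** Two dose levels fix a two-parameter curve exactly and leave nothing to test its shape. No observation lies above 1.0 mg/kg.

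**The case against.** The strongest reply is that the sentence is background. It is hedged, it credits outside blood data, and no planned result depends on it. The stated objective is to measure ketamine in milk, and within the study resumption of breastfeeding rests on the first subject's measured samples. Much of this stands, and it keeps the point small. It does not remove it, because the sentence sits in the design summary, has no source, and presents the step from blood to milk as settled.

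Several stronger readings are tempting and are not supported:

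- *The protocol claims that its design enables the extrapolation.* It does not; it credits the linearity of blood levels.
- *Blood sampling is needed.* Milk is measured directly at both doses, so a milk dose ratio needs no blood. Blood would be needed only to check that the milk-to-blood relation is constant.
- *Each woman supplies a single ratio.* She supplies several, at matched times and for two analytes. They are correlated, so the number of independent units stays at the number of women.
- *Simple doubling could be wrong by 1.56-, 1.94- or 2.90-fold.* Those factors describe the imprecision of a freely estimated ratio. They do not measure the error of proportional scaling.

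It is also fair to note that the background puts anaesthetic doses at 1 to 3 mg/kg (route not stated), which overlaps the range being extrapolated to. That helps for blood but says nothing about milk.

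**Conclusion.** The point holds as one about an unsupported claim and a missing descriptive check. The protocol presents milk estimates above 1.0 mg/kg as available on the strength of unsourced blood linearity, and the study as planned neither verifies the blood-to-milk step nor observes any higher dose. If the ratio were analysed, four women would give 95% limits of about 1.56-, 1.94- or 2.90-fold either way. These figures rest on assumed within-woman CVs of 20%, 30% and 50%, four complete pairs and log-normal variation. A CV near 10% would tighten the factor to 1.25; fewer women would widen it.

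A reader might infer that no estimate above 1.0 mg/kg can ever be given, or that scaled values would be too low. Neither follows. A scaled estimate is possible if its assumption is declared, and nothing in the documents shows the direction of any error. The order confounding is a limit on interpretation; no session effect has been shown.

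**What to change.** 1. **Summary of Research Design.** Replace the extrapolation sentence with wording such as: *Conclusions apply to the doses studied. Any estimate for a higher dose assumes that milk concentration is proportional to dose, which this study does not verify, and will be shown with its uncertainty.* If a source for blood linearity is kept, cite it with its route and dose range.
2. **Data Analysis.** Add the within-woman 1.0:0.5 milk concentration ratio at matched times, for ketamine and norketamine separately. Show each woman's ratios, and at each time give the geometric mean with a 95% interval based on the number of women. Call it a descriptive check, state that dose and session order are confounded, and report how many pairs are missing because a sample was not analysed or was below quantification.
3. **Dose units.** The Summary of Research Design and Procedures say "Two dosages will be administered: 0.5ml/kg and 1.0ml/kg". The timing chart uses mg/kg, and the same summary says "The dosage range for a 50 kg woman amounts to 25-50mg", which is also mg/kg arithmetic (25/50 = 0.5; 50/50 = 1.0). These statements must be reconciled, because the dose axis and the reference ratio of 2 presuppose one consistent unit.

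The cost is a weaker claim about higher doses and a short extra table. No further samples are needed, and no dose or clinical rule is proposed.

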1-3 hours	Support for subject and integration of experience
3 hours	BP, HR, Second Pump
3-6 hours	Subject relaxing at Study Site
6 hours	Third Pump
9 hours	Fourth Pump
12 hours	Fifth Pump if necessary (as per procedure)
Home	Milk has been quantified for volume at each pump and an aliquot labelled, saved and refrigerated. If subject has gone home earlier—at 6 hours or later, subject will be contacted to pump at the assigned intervals and an aliquot refrigerated for pickup and delivery to the clinical lab for analysis.

Safety: Administration of ketamine will occur in office premises and with standard of care safety equipment available. This includes CPR trained personnel, ambu bag, defibrillator and a suction device. MDs will be present on site throughout and will administer the injections.

Injections are provided with a 25 gauge, 1 inch needle using ketamine in a sterile 100mg/ml concentration. Total volume of ketamine fluid will be less than 1 cc. Occasionally, there may be a slight bleed from the injection site. There may be mild ache at the injection site for up to a few hours. Injections are intra-muscular and into the deltoid or buttocks regions.

Subjects will be provided in advance for preliminary screening with our standard intake form to assess current and previous illnesses, psychiatric conditions, and emergency contacts, etc. This will enable Investigators to screen potential subjects prior to enrollment—as is our general practice. The Informed Consent will be provided along with the Intake Form for review by the subjects prior to making a decision to proceed with the study intake process.

At Intake, subjects will discuss, and make a decision to sign, or , the Informed Consent.

HIPAA confidentiality will be maintained throughout. Subjects will be given a numerical designation for all materials, other than the written forms discussed herein. All written and confidential materials will be stored in a locked file on premises available only to the Investigators.

No hazardous substances or procedures are involved

Methods

Quantitative analysis of ketamine will be performed by [name] PhD, Professor of Laboratory Medicine at UCSF School of Medicine and [name] at UCSF.

- 1) Lab will prepare a standard for analysis of ketamine and its principle metabolite norketamine in breast milk. The half-life of ketamine is 2.1 hours, and that of norketamine 1.2 hours (Herd et al 2007). The study will view the half-life as being a conservative 3 hours.

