1. 5) Each aliquot will be labelled with coded subject designation, concentration of ketamine administered, date, and interval. The lab will be provided with the actual quantity of ketamine administered to each subject at the 0.5 and 1.0mg/kg levels and the weight of each patient in kgs.
 - 1)
1. 6) The Lab will provide the data to KRF in formats suitable for journal publication.

INTAKE FORM ATTACHED

AS PREVIOUSLY INDICATED THERE ARE NO QUESTIONNAIRES BEING ADMINISTERED— THIS WAS DELETED FROM THE PRIOR REVISION

Inclusion Criteria

- Age 21-45
- Postpartum with established lactation for a minimum of 3 months.
- Ability to pump breast milk and to provide a reservoir for infant feeding prior to the study; or acceptance of bottle feeding by the infant.
- In good health—normal BP/P; afebrile-temp ascertained; review of systems by MD; absence of diagnosed illnesses.
- Not pregnant--Pregnancy tested for before each administration by urine assay.

Exclusion Criteria:

- Hypertension with a BP greater than 145/90
- Absence of all psychiatric medications specifically; medications and supplements, or evaluated by the PI for non-interference
- No alcohol or other substances such as marijuana for 72 hours or more.
- Weight <50kg or > 90kg.
- Pregnancy

Potential Adverse Effects

- • Nausea and vomiting—a less than 5% incidence of intolerability to ketamine.
- • Transient hypertension—BP will be monitored. In clinical practice, and in this age group, this has not occurred with any frequency.
- • Ketamine is a dissociative anesthetic and subjects have a high likelihood of experiencing dissociative effects during the first two hours following ketamine's administration. Generally, the major impact occurs in the first hour, with full recovery to baseline by 3 hours. The Investigators have conducted thousands of sessions in which dissociative effects are part of the ketamine assisted

psychotherapy (KAP) approach, including at much higher doses than those being administered in this study. Subjects may experience, an altered mental state in which there is an imaginative stream of associations, sensations and imagery. There can be anxiety accompanying a shift from ordinary reality. The Investigators have specialized in developing a transformative psychotherapy with utilization of this state and are fully equipped and experienced in dealing effectively with this state. Subjects will be prepared for the possibility of this

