- experience. Administration will be conducted in the same comfortable setting in which KAP sessions are routinely provided. Investigators are continually present throughout the time frame of this experience, however long it may persist. Subjects will remain in the office until fully recovered and will have a ride home and will not drive themselves.

- • Agitation—may occur transiently with dissociative effects. Subjects will remain in the clinical setting until ketamine’s influence has passed and they are safe to leave. We have never had to treat agitation, as it passes, and reassurance and support have been sufficient to enable attainment of calmness. In the event of unusual agitation that is a risk to the patient, sublingual lorazepam can be administered. With over 500 patients and several thousand ketamine sessions, this has never occurred.
- • Safety in operating machinery and driving—Subjects will have rides home when ready to leave.
- • No long term negative effects involving administration of ketamine in these dosages and frequencies have been reported in vast numbers over many decades of use.

A follow-up formal telephone session will occur at 4 weeks after the second administration. Questions will focus on any adverse effects on subjects or infants, difficulties in resuming breast feeding, psychological difficulties and insights not discussed in the prior 4 weeks of follow-up availability. Throughout the study, subjects will be reachable by their cell phones for emergency and consultative contact with the Investigators—who will have developed an on-call schedule.

Potential Benefits to Subjects

Ketamine administered in this clinical environment may well contribute to a sense of well-being and an exploration of consciousness. If emotional issues arise these will be fully processed. The Study Staff are skilled psychotherapists, versed in the practice of ketamine assisted psychotherapy.

Subjects may well feel they are contributing to the benefit of women who have postpartum symptoms and disorders.

Method of Subject Identification and Recruitment

Two of the investigators have close connections to practicing OB/GYNs, one being one of these himself; and the other has a practice with postpartum women in part at a local

university medical school. As only 4 subjects will take part, with the possibility of drop-out requiring further recruitment this 'n' is compatible with the outreach potential of the Investigators.

No advertising is involved.

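### The post-dose blood pressure reading falls 60 minutes after injection in the text but 45 minutes on the chart, and no timed reading comes before it

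*Combined protocol and SAP*

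**What the plan says.** Procedures fixes one post-dose cardiovascular check and gives its purpose: "BP and PR will be performed at 1 hour post-administration to assess peak impact on cardiovascular status". Its clock starts at administration.

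The Procedure Timing Chart uses another clock. Its zero is the baseline pump. The injection row, "IM 0.5mg/kg; or Second Session 1.0mg/kg", stands at 15 with no unit printed. The next row, 15-60, lists only "Support for Subject who is reclining on sofa with eyeshades and ambient music". BP and heart rate follow at 1 hour, and the 3-hour row reads "BP, HR, Second Pump". The only earlier BP/HR row is the pre-dose one, taken here as -15 minutes because its label contains a misprint. Further pumps are at 6, 9 and, if needed, 12 hours.

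Elsewhere, Summary of Research Design gives the onset of intramuscular effect as 2-5 minutes. Potential Adverse Effects says "Transient hypertension—BP will be monitored", with no times or frequency. It also says "Investigators are continually present throughout the time frame of this experience, however long it may persist". Safety places MDs and resuscitation equipment on site throughout. Exclusion Criteria lists "Hypertension with a BP greater than 145/90".

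**The concern.** Staff who follow the text and staff who follow the chart would take the same named reading at different times after the dose. Neither place says which clock governs.

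The reading is also the first timed one after the injection. The protocol expects an effect within minutes and lists transient hypertension as a potential adverse effect. Its Background also reports transient hemodynamic changes, mainly raised BP, in one third of patients in pooled trials. Those were intravenous data, so they are context and not a rate for this study. The protocol gives no reason for leaving the first 45 or 60 minutes without a scheduled reading, or for taking 1 hour as the time of greatest cardiovascular effect.

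The same clock governs the milk samples, because the second pump shares its row with the 3-hour BP/HR check. In a study whose data are concentrations at set times, time since dose should have one meaning.

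**Working it through.** **Inputs**

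- Text (Procedures): BP/PR at 60 minutes after administration.
- Chart: baseline pump at 0, injection at 15, BP/HR at -15 minutes, 1 hour and 3 hours, pumps at 3, 6, 9 and 12 hours.
- Methods: ketamine half-life 2.1 hours, treated conservatively as 3 hours.
- Summary of Research Design and Procedures: 4 women, 2 dosing sessions each.

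**Unit of the injection row.** The chart prints 15 without a unit. Minutes is the only reading that fits the next rows, which run 15-60, then 1 hour, then 1-3 hours.

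**Can the text's 60 minutes be reproduced from the chart?** Time after injection = chart time - 15 minutes. For the 1-hour row, 60 - 15 = 45 minutes. The text's figure is not reproduced, and the difference is 60 - 45 = 15 minutes.

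**Alternative reading.** Suppose the 1-hour row means one hour after injection. It would then stand at chart minute 15 + 60 = 75. That leaves a gap after the 15-60 row, overlaps the 1-3 hour row and departs from the chart's own zero. It is not the natural reading.

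**All rows, converted to time from injection**

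| Chart row | Chart time | Time from injection |
|---|---|---|
| Arrival | -30 min | -30 - 15 = -45 min |
| Pre-dose BP/HR | -15 min | -15 - 15 = -30 min |
| Baseline pump | 0 | 0 - 15 = -15 min |
| First post-dose BP/HR | 60 min | 60 - 15 = 45 min |
| BP/HR and second pump | 180 min | 180 - 15 = 165 min (2.75 h) |
| Third pump | 6 h | 6 - 0.25 = 5.75 h |
| Fourth pump | 9 h | 9 - 0.25 = 8.75 h |
| Fifth pump, if needed | 12 h | 12 - 0.25 = 11.75 h |

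**Timed BP/HR readings between injection and the first post-dose reading.** None, over 45 minutes on the chart or 60 minutes by the text.

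**What 15 minutes means for a milk concentration (illustration).** Assume that ketamine in milk declines exponentially with the half-lives in Methods. The documents give no milk half-life. A sample taken 0.25 hours earlier would be higher by a factor of 2^(0.25/half-life):

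- 3 hours: 2^(0.25/3) = 1.06, about 6%.
- 2.1 hours: 2^(0.25/2.1) = 1.09, about 9%.

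**Cost of added readings.** 4 women x 2 sessions x 1 or 2 readings = 8 or 16.

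**The case against.** The strongest reply is that the Procedures sentence need not promise a peak found from a series of readings. It can mean one check at the time when the investigators expect the greatest effect. That reading is fair. A reader might infer that the schedule misses the BP peak, or fails its stated purpose. The documents do not support that, because they nowhere say when BP peaks and so do not show 45 or 60 minutes to be wrong.

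Nor does this sentence settle the matter: "Generally, the major impact occurs in the first hour, with full recovery to baseline by 3 hours". It is about dissociative effects, not BP. Even if it were borrowed for BP, both 45 and 60 minutes lie within or at the end of the first hour, and the 3-hour check matches the stated recovery time.

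It would also be wrong to infer that BP goes unwatched. The chart has three timed checks per session, one of them at 3 hours. Untimed monitoring is promised, investigators stay with the subject, MDs are on site, and women with raised BP are excluded. The protocol adds that hypertension has not been frequent in this age group in clinical practice. These safeguards reduce the risk, but none sets a reading time or says which clock applies.

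Finally, the practical effect is small. No dose, stopping rule or listed analysis uses the 1-hour reading. A constant offset leaves an estimated half-life unchanged under exponential decline, and times from dose can be recovered if actual clock times are recorded. That stands, although Methods lists only date and interval as the timing information on the aliquot labels.

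**Conclusion.** Two things hold. The text and the chart give different times for the same reading, 60 and 45 minutes after injection, and nothing else in the documents resolves the difference. No timed BP or heart rate is scheduled between the injection and that reading, and the protocol gives no reason for the gap.

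The timing is therefore unjustified. It is not shown to miss a peak or a rise in BP. Confidence is high for the clock conflict and for the absence of a timed early reading. Both rest on reading the chart's 15 as minutes and its 1 hour as counted from the baseline pump.

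Severity is minor. The milk-concentration objective does not depend on BP and is affected only by the 15-minute uncertainty in what a sample time means. That is roughly 6% to 9% of a single concentration under the assumed decline.

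**What to change.** Set time zero at the injection for every chart row, print units, and state in Procedures and Methods that all times run from the injection:

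- arrival at -45 minutes, pre-dose BP/HR at -30 minutes, baseline pump at -15 minutes
- injection at 0
- BP/HR at 60 minutes
- BP/HR and second pump at 3 hours
- later pumps at 6, 9 and, if needed, 12 hours

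Add one or two cuff readings in the first 45-60 minutes, taken by the MDs already present. About 15 and 30 minutes would serve as an example; the documents do not point to particular times. Keep the 1-hour and 3-hour readings. Removing the word peak from the text would make the wording safer, but on its own it would leave both the two clocks and the early gap in place.

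The cost is an edit to the chart and a little text, 8 to 16 extra cuff readings in the whole study, and some disturbance to a subject reclining with eyeshades. Each session becomes about 15 minutes longer. Arrival to the 9-hour pump would take 9 h 45 min instead of 9 h 30 min, which still fits the minimum of 10 hours given in the Screening Script.
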